6.2.3 Cycles 2 and Higher

Patients will receive selpercatinib 160 mg BID in continuous 28-day cycles until PD, unacceptable toxicity, or other reasons for treatment discontinuation. Patients with documented PD may be allowed to continue selpercatinib if the patient is tolerating treatment and, in the opinion of the Investigator, the patient is deriving clinical benefit from continuing study treatment, and continuation of treatment is approved by the Sponsor. Additionally, the patient must re consent prior to continuing to receive study treatment.

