7.3 Cycles 2 and Higher

The following procedures will be performed prior to dosing as noted. Routine clinic visits performed within ± 2 days of the nominal visit day will not be considered protocol deviations.

- Symptom-directed physical examination, weight, and ECOG: Day 1 each cycle starting with C2.
- Vital signs: up to 4 hours pre-dose on Day 1 each cycle starting with C2.
- Resting 12-lead ECG (2 hours [± 10 minutes] post-dose on C2D1, C3D1, C4D1, C5D1 and C6D1 and every 12 weeks thereafter). Additional ECGs may be performed if clinically indicated.
- Blood sample of population PK (2 mL whole blood) for all enrolled subjects: each cycle D1 predose.
- Serum or urine pregnancy test for women of childbearing potential (surgically sterilized females or those who have not experienced menses for at least 2 years are not required to be tested): Day 1 each cycle starting with C2.
- Hematology: (as described in Section 7.1). Day 1 each cycle starting with C2.
 - Note: Patients found to have treatment-emergent hematologic toxicity of Grades 3 or 4 will be monitored at least weekly until resolution.
- Serum chemistries (as described in Appendix H): Day 1 each cycle starting with C2.
 - Note: Patients found to have treatment-emergent laboratory toxicity of Grades 3 or 4 will be monitored at least weekly until resolution.
- LFTs, including AST, ALT, ALP, and total and direct bilirubin: C2D15 and C3D15.
- Thyroid panel: Day 1 of odd-numbered cycles, starting with C3.
- Urinalysis: D1 C2, and as clinically indicated.
- Dispense selpercatinib.
- Selpercatinib administration.
- Outpatient diaries for recording daily selpercatinib dosing, H2 blockers and antacids.
- AEs.
- Concomitant medications.
- Patient-reported outcomes:
 - For MTC patients with diarrhea present at baseline: bowel diary, Day 1 each cycle starting with C2.
 - EORTC QLQ-C30, completed at the same cycle visits as disease assessments until EOT.

The following procedures will be performed as planned even if cycles are delayed. As a result, the following procedures may not always occur at the beginning of a cycle.

- Calcitonin, CEA: for patients with MTC only; Day 1 of C2 and odd-numbered cycles, starting with C3 through C13, and every 12 weeks thereafter (± 7 days of each radiologic disease assessment). For each patient, all tests for calcitonin and CEA should be performed in the same laboratory to minimize intra-patient, lab-to-lab variability in their measurement.

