7.7.4 Collection of EORTC QLQ-C30 and Bowel Diary

Paper Quality of Life (QoL) instruments will be administered pre-dose on C1D1.

The EORTC QLQ-C30 and a bowel diary (for MTC patients only) will be used (refer to [Appendix J](#)) and should be implemented for newly enrolled patients. Only patients who have completed the questionnaire at baseline should complete subsequent questionnaires at the specified follow-up periods.

For EORTC QLQ-C30, subsequent assessments will occur at the same cycle visits as disease assessments until EOT. Each assessment should be performed before the subject learns the results of his or her restaging.

For MTC patients, the bowel diary assessments will be collected weekly on Cycle 1, and on Day 1 of every cycle thereafter through EOT. Inaccurate recording will not be considered a protocol violation.

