6.5. Patient Disposition

A detailed description of patient disposition will be provided. It will include a summary of the number and percentage of patients entered into the study, enrolled in the study, reasons for discontinuation from study treatment, and reasons for discontinuation from the study. Reason for discontinuation from both study treatment and the study will be listed by the pre-determined categories. If the reason for discontinuation is adverse event (AE) or death, the associated AE or cause of death will be reported. All patients entered in the study will be included in the summary.

The number and percentage of patients will be summarized by the enrolling study center. In the event a patient transferred to another center during the study, the center of original enrollment will be used for this tabulation.

Patients with progressive disease may be allowed to continue study drug if, in the opinion of the Investigator, the patient is deriving clinical benefit from continuing study treatment, and continuation of treatment is approved by the Sponsor. The number and percentage of such patients continuing to receive study drug after the documentation of disease progression will be presented.

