Similarly, number and proportion of patients experiencing definite worsening (defined as the first worsening from baseline, a ≥ 10 point decrease, without any further improvement of ≥ 10 points) and time to definite worsening will also be summarized.

Time to first improvement and to first worsening, respectively, will be evaluated using Kaplan-Meier method. For time to first improvement, patients who did not improve will be censored at

the date of their last EORTC assessment; Similarly, for time to first worsening, patients who did not worsen will be censored at the date of their last EORTC assessment.

Questionnaire compliance will be summarized. Compliance rates will be calculated at each assessment time point. Compliance at an assessment time point is defined as the number of patients who were assessed divided by the expected number of patients at that time point. The expected number of patients:

- at baseline is equal to the number of patients enrolled
- at any post-baseline visit is equal to the number of patients who are alive and have not progressed

A patient who answers at least one item at a time point is considered to have been assessed. Reasons for non-compliance will be tabulated by assessment time point.

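### QLQ-C30 compliance counts expected forms by progression status while the protocol collects them by treatment status, so the rate can be misstated in either direction

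*SAP*

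**What the plan says.** SAP 6.10.1 sets compliance at each time point as a ratio, "defined as the number of patients who were assessed divided by the expected number of patients at that time point". The numerator rule is broad: "A patient who answers at least one item at a time point is considered to have been assessed". The denominator is the number enrolled at baseline; afterwards it "at any post-baseline visit is equal to the number of patients who are alive and have not progressed". The SAP does not say whether progression is by independent review or by investigator, and it does not require the patient to be on treatment.

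The protocol sets collection differently. Section 7.3 has "EORTC QLQ-C30, completed at the same cycle visits as disease assessments until EOT", and Section 7.7.4 repeats that "subsequent assessments will occur at the same cycle visits as disease assessments until EOT". Section 7.4 and Table 7-1 add a form at the EOT visit. Section 7.7.4 also states: "Only patients who have completed the questionnaire at baseline should complete subsequent questionnaires at the specified follow-up periods".

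Progression does not necessarily end treatment. Under Section 6.2.3, "Patients with documented PD may be allowed to continue selpercatinib if the patient is tolerating treatment", subject to further conditions. Footnote w to Table 7-1 continues scans for such patients until a second progression. SAP 6.5 expects the group to exist: "The number and percentage of such patients continuing to receive study drug after the documentation of disease progression will be presented".

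**The concern.** The two documents use different clocks. The form stops when treatment stops; the expected count stops at progression. Two groups fall between them.

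- **Off drug, alive, no progression.** No form is due after EOT, yet these patients stay in the denominator and look like non-compliers.
- **Form completed after progression.** This covers patients treated beyond progression and patients attending EOT because they progressed. They are due a form but are not in the denominator. Read as written, the numerator still counts them.

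A smaller third group has no baseline form. The protocol asks these patients not to complete later forms, but the SAP keeps them as expected.

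The rate matters because apart from item proration within scales, missing questionnaire data are not imputed, and the summaries use patients who report data. The compliance table is therefore the reader's main guide to how much is missing. A rate that moves with the mix of off-drug and post-progression patients cannot do that job reliably.

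**Working it through.** The documents state no compliance figure, so there is nothing to reproduce. The check is whether the SAP ratio returns the true completion rate among patients due a form.

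**Notation at one visit**

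- a = on treatment, not progressed
- b = on treatment after first progression
- c = off treatment, alive, not progressed
- q = true completion rate among patients due a form

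Forms due under the protocol: a + b. Forms received: q(a + b). Expected under the SAP: a + c.

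- SAP rate = q(a + b)/(a + c)
- Rate matched to the collection schedule = q(a + b)/(a + b) = q

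The SAP rate equals q only when b = c. It exceeds 100% when q(a + b) > a + c. This rearranges to qb > (1 − q)a + c, meaning that post-progression completers outnumber non-completers in the denominator. Equivalently, b > [a(1 − q) + c]/q.

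**Illustrations (all counts are assumptions)**

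| a | b | c | q | Received q(a+b) | SAP denominator a+c | SAP rate | Matched rate |
|---|---|---|---|---|---|---|---|
| 40 | 3 | 0 | 95% | 40.85 | 40 | 102.1% | 95% |
| 40 | 6 | 2 | 95% | 43.70 | 42 | 104.0% | 95% |
| 40 | 2 | 8 | 95% | 39.90 | 48 | 83.1% | 95% |
| 40 | 5 | 5 | 95% | 42.75 | 45 | 95.0% | 95% |
| 48 | 2 | 8 | 100% | 50 | 56 | 89% | 100% |
| 42 | 8 | 2 | 100% | 50 | 44 | 114% | 100% |

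**Threshold for passing 100% with a = 40, c = 0**

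- q = 95%: b > 2/0.95 = 2.1
- q = 90%: b > 4/0.90 = 4.4
- q = 85%: b > 6/0.85 = 7.1

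Each off-drug patient without progression raises the threshold by 1/q. With c = 2 and q = 95% it is (2 + 2)/0.95 = 4.2.

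**The EOT visit.** Protocol 6.4 lists progression among the reasons to stop treatment, so many EOT attendees may already have progressed. Assume 30 attendees, k of them progressed, and apply the SAP denominator to those attendees. The rate is then 30q/(30 − k).

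- k = 10: 105% at q = 70%, 135% at q = 90%
- k = 25: 420% at q = 70%, 540% at q = 90%

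EOT falls at a different time for each patient, and the SAP does not say over whom its denominator would be counted there. These figures hold only on the reading just stated.

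**A further route.** Section 7.7.4 has the form completed before the patient learns the restaging result. If progression is dated to that visit, a patient who progresses there has completed a form and is not in the expected count.

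**The case against.** The strongest reply has five parts.

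1. **The errors offset.** When b = c the SAP rate is exact, and the documents give no counts from which to predict direction or size. This stands. A reader might infer that the reported rate must be wrong; the documents support only that it can be.

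2. **A rate above 100% is conditional.** Stopping at progression is the default. Continuing requires tolerability, investigator-judged benefit, sponsor approval and re-consent. At ordinary visits post-progression completers must outnumber every non-completer in the denominator, including those off drug. This also stands. Nor does collection until EOT produce the excess by itself, since off-drug patients only lower the rate. The excess comes from treatment beyond progression, the EOT form, and forms completed at the visit that shows progression.

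3. **The numerator may be meant as assessed among expected.** That reading caps the rate at 100%. The sentence defining who counts as assessed has no such limit, so the literal reading is the more natural one, but the text does not exclude the other. Under the capped reading, forms due after progression drop out of compliance altogether and off-drug patients still lower the rate.

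4. **Part of this is convention.** Keeping living, progression-free patients in the denominator, with or without a baseline form, measures data availability. That is a legitimate quantity, and the missing-baseline point is partly a matter of choice. But it is not compliance with the collection schedule, which is what the table is called.

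5. **Reasons for non-compliance are tabulated.** This may make off-drug patients visible, although the categories are not given. It does not correct the rate, and it would require reasons for patients who owed no form.

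**Conclusion.** The mismatch is real and follows from reading SAP 6.10.1 beside Protocol 7.3, 7.4 and 7.7.4. Nothing in either document stops the form at progression, limits the numerator to progression-free patients, or removes off-drug patients without progression from the denominator.

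The supported conclusion is that compliance can be misstated either way. In the illustrations it runs from about 12 points too low (83.1% against 95%) to 14 points too high (114% against 100%) at ordinary visits. A rate above 100% is possible there and most plausible at EOT. All sizes rest on assumed counts and on the literal reading of the numerator.

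A reader might go further and infer that the questionnaire results are invalid or that efficacy conclusions are affected. The documents do not support that: patient-reported outcomes are exploratory, compliance is descriptive, and neither the questionnaire scores nor the response rate uses this denominator. This is a minor point, worth correcting because correction is cheap.

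**What to change.** Replace the post-baseline denominator in SAP 6.10.1. Expected at a time point should mean patients with a baseline questionnaire for whom a form is due under the protocol at that time point: those who reached the scheduled visit while on study treatment, including beyond progression, or who are due the EOT visit. State that the numerator counts only those same patients, and report EOT as its own row. The rate then equals q and cannot exceed 100%; each row of the table above returns 95% or 100% as it should.

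If the sponsor also wants availability among living, progression-free patients, show it separately under that name, restrict its numerator to the same patients, and say whether progression is by independent review or investigator.

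The cost is one or two lines of SAP wording and a change to one table program. It needs no new data and changes no trial procedure.

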6.10.2. Bowel Diaries

The bowel diary questionnaire is a modified version of the STIDAT (Systemic Therapy Induced Diarrhea Assessment Tool), a standardized patient-reported questionnaire used to assess systemic therapy-induced diarrhea in oncology patients (Lui et al. 2017). The questionnaire used in this study contains 11 questions and assesses the patient's perception of having diarrhea, daily number of bowel movements, daily number of diarrhea episodes, the presence of urgency, presence of abdominal discomfort, fecal incontinence, patient's perception of diarrhea severity, and QoL. In the case of missing items in the QoL subscale, the scale will be excluded from the analysis and no imputation will be made.

This questionnaire uses a weighted scoring system, which will not be applied in this study due to the modification of the tool used in this study that invalidates the weights and could produce incorrect findings.

The mean/SD and median/range total QoL score, mean (SD) number of bowel movements (item 3), mean (SD) number of diarrheal episodes (item 2), and number/proportion of patients experiencing diarrhea (item 1), categorical response to severity of diarrhea (item 1 for those with diarrhea), urgency (item 4), abdominal discomfort (item 5), and fecal incontinence (item 6), respectively, will be summarized descriptively at each time point at which the data were collected for all patients, and separately for those who had diarrhea at baseline.

Item level mean/SD and median/range values will be reported for each QoL scale (items 8-12) at each study visit. Additionally, mean scores across time will be presented in a line plot for items 8-12. Change of score from baseline will also be summarized for each scale at each visit, and be presented in a line plot.

Worsening on the bowel diary is defined as any stepwise categorical decline in the diarrhea item 1 (such as, no diarrhea to minimal, moderate or severe; minimal to moderate or severe; moderate to severe), and improvement is defined as any stepwise improvement (such as minimal to no diarrhea, moderate to minimal or no diarrhea, severe to moderate, minimal or no diarrhea).

For all change-from-baseline measures, the analysis set will include all treated patients who have baseline and at least one post-baseline PRO assessment on the item being evaluated.

The number and proportion of patients experiencing worsening or improvement from baseline will be reported at each study visit at which the bowel diary is collected. Kaplan-Meier method will be used to evaluate time to first improvement (among the baseline diarrhea population) and time to first worsening (for the entire Cohort 2), respectively. For patients in the baseline diarrhea population, those who didn't experience any improvement or worsening will be censored at the date of their last bowel diary assessment. For patients in Cohort 2 who didn't have diarrhea at baseline, time to first worsening will be censored at the date of data cutoff.

For patients with improvement, the duration of improvement (defined as time from first improvement to the return to or below the baseline categorical level) will be reported as median, range, mean/SD days. Similarly, the duration of worsening (defined as time from first worsening to the return to or above the baseline categorical level) will be reported as median, range, mean/SD days.

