HRQoL instruments (European Organization for Research and Treatment of Cancer Quality of Life Questionnaire-Core 30 [EORTC QLQ-C30]) will be administered pre-dose on C1D1 and subsequent assessments will occur at the same cycle visits as disease assessments until EOT. For MTC patients with diarrhea present at baseline, bowel assessments will be collected pre-dose C1D1, weekly for the first cycle, and at D1 of each cycle until EOT.

STUDY ENDPOINTS:

Primary Endpoint:

- ORR based on RECIST v1.1 assessed by IRC.

Secondary Endpoints:

- Parameters of anti-tumor activity/clinical benefit, including: ORR (by Investigator), DOR (by IRC and Investigator), CNS ORR (by IRC), CNS DOR (by IRC), TTR (time to response), TTBR (time to best response by IRC and Investigator), CBR (by IRC and Investigator), PFS (by IRC and Investigator), and OS.
- Frequency, severity, and relatedness of treatment-emergent adverse events (TEAEs) and Serious Adverse Events (SAEs), changes in hematology and blood chemistry values, assessments of physical examinations, vital signs, and ECGs.

- Plasma concentrations of seliperatinib and PK parameters, including, but not limited to, AUC_{0-24} , C_{max} , and T_{max} .

Exploratory Endpoints:

- Differences in efficacy and safety based on seliperatinib PK parameters.
- Changes in CEA and calcitonin (for patients with MTC), thyroglobulin (non-MTC patients), ACTH and cortisol (patients with Cushing's disease related to their cancer) with seliperatinib treatment.
- Changes from baseline in disease-related symptoms and HRQoL, as measured by EORTC QLQ-C30 (adults), and patient bowel diaries (MTC patients only).
- Time from PD₁ to PD₂ for patients who continue to receive study treatment beyond disease progression.

STATISTICAL METHODS:**Safety Analyses:**

The safety population will consist of all enrolled patients who receive at least one dose of seliperatinib. A baseline measurement and at least one laboratory or other safety-related measurement obtained after treatment of study drug may be required for inclusion in the analysis of a specific safety parameter.

Efficacy Analyses:

The efficacy analysis will be conducted on all treated patients enrolled in Cohort 1 and 2 who have confirmed *RET* fusion positive solid tumor or *RET* mutant MTC by central lab, respectively.

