| Confirmatory disease assessment ^z | | | | | | At least 4 weeks post 1 st PR | | | |
| Blood sample for intensive PK ^{aa} | | X | X | | | | | | |
| Blood sample for PopPK ^{bb} | | X | | | | D1 of each cycle Predose sample to be drawn | | | |
| EORTC QLQ-C30 ^{cc} | | X | | | | Every 8 weeks (±7 days) starting with D1 C3 through D1 C13. Every 12 weeks (±7 days) thereafter | X | | |

| Visit Window | Screening | Cycle 1 | | | | Cycle 2-higher | SFU ^b | | LTFU ^c |
|--|-----------------------------------|---------------|---------------|----------------|-----------------------------|----------------------|------------------------------|-----------------|-------------------|
| | Up to 28 days prior to first dose | D1 ±2 Days | D8 ±2 Days | D15 ±2 Days | D22 ^d ±2 Days | ±2 Days | EOT ^a ≤ 7 days | D 28 ±7 days | |
| Dispense selpercatinib | | X | | | | D1 of each cycle | | | |
| Selpercatinib administration | | | | | | | | | |
| Patient dosing diary | | | | | | | | | |
| Patient bowel diary (MTC only) ^{dd} | | X | X | X | X | D1 C2, 3, 4, 5, etc. | X | | |
| Adverse events ^{ee} | | | | | | | | | |
| Concomitant medications ^{ff} | | | | | | | | | |
| Survival ^{gg} | | | | | | | | X | X |

Abbreviations (for Table 7-1 and Footnotes): ACTH-adrenocorticotrophic hormone; AE-adverse event; ALP-alkaline phosphatase; ALT-alanine aminotransferase; AST-aspartate aminotransferase; BUN blood urea nitrogen; C-cycle; CEA carcinoembryonic antigen; CR complete response; CT-computed tomography; D-day; ECG electrocardiogram; ECOG-Eastern Cooperative Oncology Group; EORTC QLQ-C30-European Organization for Research and Treatment of Cancer Quality of Life Questionnaire-Core 30; EOT-End of Treatment; IV intravenous; LDH lactate dehydrogenase; LTFU long-term follow up; MTC medullary thyroid cancer; MRI magnetic resonance imaging; PD-progressive disease; PK pharmacokinetics; PR partial response; RBC-red blood cell; SAE-serious adverse event; SFU safety follow-up; TSH-thyroid-stimulating hormone; T3-free triiodothyronine; T4-free thyroxine; WBC white blood cell.

- End of Treatment (EOT): +7 days of the last dose or the decision to terminate treatment. If lab testing is performed ≤7 days prior to EOT, repeat testing does not need to occur on EOT.
- Safety Follow-Up (SFU): 28 days (±7 days) after last dose of study drug.
- Long-Term Follow-Up (LTFU): approximately every 3 months (±1 month) for up to two years after the last dose of study drug.
- Telephone contact for safety.

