- x. If not performed within the last 8 weeks.
- y. Patients who discontinue study drug for reasons other than PD (e.g., AE, noncompliance, etc.) may (but for practical reasons and to minimize patient inconvenience, are not required to) undergo additional disease assessment by imaging (as specified above until PD, withdrawal of consent or initiation of a new anticancer therapy(ies)).
- z. Confirmatory scans: Minimum of 4 weeks (e.g., 28 days) after the first tumor evaluation showing a CR or PR by RECIST 1.1, if permitted by regulatory authorities. The next scan should continue according to the schedule above.
- aa. For 12 subjects in intensive PK testing, PK test performed on C1D1: Up to pre-dose, and post-dose 1 hour (± 15 minutes), 2 hours (± 15 minutes), and 4 hours (± 15 minutes), 8 hours (± 30 minutes) and 12 hours (± 30 minutes), C1D8: Up to pre-dose, and post-dose 1 hour (± 15 minutes), 2 hours (± 15 minutes), and 4 hours (± 15 minutes) and 8 hours (± 30 minutes).
- bb. For all enrolled subjects in PopPK testing, PK test performed on each cycle D1 predose.

- cc. EORTC QLQ-C30. The questionnaires should be answered by the subject to the best of his/her ability, prior to receiving drug on C1D1 and preferably prior to learning the results of the radiologic disease assessment for subsequent cycles.
- dd. Only for patients with a diagnosis of MTC and diarrhea at baseline. Two patient bowel diary cards will be dispensed on C1D15. The questionnaires should be answered by the subject to the best of his/her ability.
- ee. AEs and SAEs should be recorded from the time that written informed consent has been obtained through the SFU Visit.
- ff. Concomitant, ongoing medication(s) plus those administered within 14 days prior to the planned start of treatment.
- gg. Patients will be followed for survival status, date of progression, and subsequent anticancer therapy(ies) by telephone or other method.

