6.1. General Considerations

6.1.1. Analysis Populations

Entered population: will include all patients who signed the informed consent form

Enrolled population: will include all eligible patients.

Safety population: will include all enrolled patients who received at least one dose of selpercatinib. This population will be used for safety analysis.

Primary efficacy analysis population/primary analysis set (PAS): will include all treated patients enrolled in Cohort 1 and 2 who have *confirmed* RET fusion positive solid tumor or RET mutant MTC by central lab, respectively. The primary efficacy analysis will be conducted on this population.

Per-protocol population: will include all patients in the primary efficacy analysis population who are compliant with the study protocol without major protocol violations.

CNS response analysis population: will include all treated patients in Cohort 1 with confirmed *RET*-fusion positive solid tumor who have IRC-assessed CNS metastases at baseline.

Baseline diarrhea population: will include patients in Cohort 2 who had diarrhea at baseline. All analyses of bowel diary will be based on this population.

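### Two exploratory patient-reported-outcome rules in the SAP are wrong as written: data-cutoff censoring in the bowel-diary worsening analysis, and the direction of QLQ-C30 definite worsening on symptom scales

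*SAP*

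**What the plan says.** **Diary analysis.** SAP 6.10.2 plans a Kaplan-Meier analysis of "time to first worsening (for the entire Cohort 2"). Patients with baseline diarrhea who have no event are censored at their last diary. For the rest, the next sentence reads: "For patients in Cohort 2 who didn't have diarrhea at baseline, time to first worsening will be censored at the date of data cutoff". SAP 6.1.1 defines a baseline diarrhea population within Cohort 2 and adds: "All analyses of bowel diary will be based on this population".

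**Who keeps a diary.** Note dd to protocol Table 7-1 says: "Only for patients with a diagnosis of MTC and diarrhea at baseline". The synopsis agrees: "For MTC patients with diarrhea present at baseline, bowel assessments will be collected pre-dose C1D1, weekly for the first cycle". So does section 7.3: "For MTC patients with diarrhea present at baseline: bowel diary, Day 1 each cycle starting with C2". The Cycle 1 and end-of-treatment visit lists (7.2 and 7.4) carry the same restriction. Section 7.7.4 does not: "For MTC patients, the bowel diary assessments will be collected weekly on Cycle 1, and on Day 1 of every cycle thereafter through EOT". SAP 6.10.2 also plans diary summaries for all patients as well as for those with baseline diarrhea, and counts a move from no diarrhea to any diarrhea as worsening. Its change-from-baseline measures require a baseline and at least one later assessment.

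**QLQ-C30.** SAP 6.10.1 defines worsening by scale type: a rise of 10 points or more on symptom scales, and a fall of 10 or more on functional and global scales. It then describes definite worsening, for each subscale, as the first worsening from baseline and adds that this means a fall of at least 10 points.

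**The concern.** A Kaplan-Meier risk set should contain only patients in whom the event could be seen, for as long as they are observed. The diary rule breaks this for patients without baseline diarrhea, and it combines two censoring conventions in one curve. It also departs from the SAP's other assessment-based analyses: QLQ-C30 time to first worsening censors at the last questionnaire, and DOR and PFS censor event-free patients at the last evaluable assessment. Where the diary rule biases the result, it understates worsening and so flatters the drug.

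The QLQ-C30 wording gives the direction of change the wrong way round for symptom scales. Depending on how it is programmed, the symptom-scale results for definite worsening would be empty or reversed.

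**Working it through.** The documents give no planned figure for either rule. The share with baseline diarrhea, worsening rates, diary durations and cutoff times below are all assumptions. Cohort 2 = 20 is the planned minimum (SAP 5.2).

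**(a) Diary, patients without baseline diarrhea have no diary.** Suppose 40% of those with baseline diarrhea worsen in months 1 to 5, their other diaries end at month 10, and cutoff is month 12. No one is censored before month 6, so the Kaplan-Meier estimate is events divided by patients at risk.

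| With baseline diarrhea | Worsened | SAP rule | Diary patients only |
|---|---|---|---|
| 5 of 20 | 2 | 2/20 = 10% | 2/5 = 40% |
| 10 of 20 | 4 | 4/20 = 20% | 4/10 = 40% |
| 15 of 20 | 6 | 6/20 = 30% | 6/15 = 40% |

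Near month 12 the SAP rule still has 15, 10 or 5 patients at risk, none with a diary.

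A simulation with staggered follow-up gives the same picture (exponential times, cutoff uniform over 8–18 months, last diary uniform over 3–14 months, true 6-month rate 30% in patients with baseline diarrhea). The estimate is about 7, 14 or 22%. It does not change whether the other patients truly worsen at 10, 30 or 50%, because their outcomes never enter it. It is close to share × rate: 0.25 × 30 = 7.5%, 0.50 × 30 = 15%, 0.75 × 30 = 22.5%.

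**(a) Diary, all MTC patients have one, events counted.** Collection ends at end of treatment, so censoring at cutoff adds unobserved time at risk. With a true rate of 30% in everyone, and 5, 10 or 15 of 20 with baseline diarrhea:

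- Last diary at 6–18 months: 30% throughout, no bias.
- Last diary at 3–14 months: 28.4, 28.9, 29.5%.
- Last diary at 1–8 months: 23.0, 24.3, 26.8%.
- Diary until end of treatment or cutoff, whichever is first, with assumed median time on treatment of 22 months: 28.2, 28.6, 29.1%. With 12 months the shortfall is about 1 to 5 points across the rates tried.

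Censoring at the last diary recovers the true cohort rate to within about 0.01 here.

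**(a) Diary, all have one, sentence taken literally.** The sentence has no condition that the patient did not worsen. With 10 patients in each group, 4 worsening among those with baseline diarrhea and 3 among the rest, the literal rule gives 4/20 = 20%; counting the events gives 7/20 = 35%.

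**(b) QLQ-C30, direction under SAP Appendix 1.**

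- Symptom item, TS = (RS−1)/3×100. Raw 2 to 3 (worse): 33.3 to 66.7, change +33.3. Raw 3 to 2 (relief): −33.3.
- Functional scale, TS = [1−(RS−1)/3]×100. Raw 2 to 3 (worse): 66.7 to 33.3, change −33.3.
- Global health, TS = (RS−1)/6×100. Raw 4 to 3 (worse): 50.0 to 33.3, change −16.7.

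A fall is therefore worsening on 5 functional scales and 1 global scale, and improvement on 9 symptom scales and items: 9/15 = 60%. If a symptom-scale patient must meet both the section's own definition of worsening (a rise) and the added description (a fall), no first worsening can qualify. If the description is programmed alone, relief is counted.

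**The case against.** **The diary conflict can be overdrawn.** A reader might take the Table 7-1 row label, "Patient bowel diary (MTC only"), as a rule that every MTC patient keeps a diary. It is not: the row carries marker dd, so note dd governs it. Likewise the endpoint wording in protocol 9.1.3, which limits the diary to MTC patients, excludes other tumors without promising a diary to every MTC patient. The real tension is section 7.7.4 and SAP 6.10.2 against the rest. This objection stands.

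**The bias may be small if everyone has a diary.** Diaries recur every 28-day cycle, so a patient still on treatment should have one within about a cycle of cutoff. The protocol reports a median DOR of 22.0 months in MTC patients naive to cabozantinib and vandetanib (1.5). If time on treatment is similar, the shortfall is 0 to 3 points. The larger figures need diaries that stop long before cutoff. This stands too.

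**The analysis-set rule may rescue the curve.** If the requirement for a baseline and a later diary governs, patients without diaries drop out and there is no dilution. But the SAP states it only for change-from-baseline measures, and the curve would then no longer describe the entire cohort.

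**The QLQ-C30 slip is recoverable.** Worsening is already defined by scale type in the same section, and a careful programmer may follow it. A reader might infer that relief will certainly be counted as worsening; the text does not support that, since it is one of two outcomes. The wording still contradicts itself.

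**Conclusion.** Both rules need correcting.

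For the diary, no reading makes data-cutoff censoring sound. Under the protocol's predominant rule, the estimate shrinks to about the baseline-diarrhea share times the rate in that group: roughly 7, 14 or 22% in place of 30% on the assumed inputs. If all MTC patients have diaries and events are counted, the bias runs from none to several points, depending on how long before cutoff the diaries stop. The literal wording would in addition drop real events.

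It is tempting to read these shortfalls against the worsening rate of the whole cohort. The documents do not allow that: where patients have no diary their rate is unobserved, and no censoring rule recovers it.

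For QLQ-C30, definite worsening contradicts itself on 9 of 15 scales and items. The size of any error depends on how many patients improve or worsen, which the documents do not give.

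Nothing here reaches ORR or any secondary endpoint. The functional and global scales, visit-level QLQ-C30 categories and QLQ-C30 time to first worsening are also unaffected.

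**What to change.** **Diary (SAP 6.1.1 and 6.10.2, with protocol 7.7.4).**

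- Reconcile section 7.7.4 and SAP 6.10.2 with note dd and SAP 6.1.1, so that one statement says who keeps a diary.
- Apply the existing requirement of a baseline and at least one later diary to time to first worsening.
- Count every observed worsening as an event.
- Censor every event-free patient at the last diary assessment, never at data cutoff.
- Label the estimate as applying to patients with a diary, which under note dd is the baseline diarrhea population, and declare this change from the entire Cohort 2.

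New diarrhea in patients without a diary is already reported through the planned adverse-event summaries by preferred term (SAP 6.11.2).

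**QLQ-C30 (SAP 6.10.1).** In the definition of definite worsening, replace the fall of at least 10 points with worsening as already defined for each scale type.

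The cost is a few sentences and one clarification of diary eligibility. No new data are needed.
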